This is a multicentre, non-interventional study to determine the rate of control of disease activity. At each site, eligible subjects will be identified consecutively as they attend scheduled clinical appointment (Day 1). Upon written consent, data regarding disease activity, treatment patterns, burden of disease and quality of life will be collected from medical records and Patient Report Outcome tools, including quality of life (SF-36, EQ-5D and IBDQ) and work productivity (WPAI) questionnaires. Retrospective data will refer to the previous three years and will include the previous IBD treatments (drug, dose, treatment duration, drug changes), and use of other health resources related with the management of IBD.

For patients with active disease at Day 1, a prospective period of 12 months will be conducted to follow up the course of the disease. Ulcerative colitis (UC) patients with no or mild disease activity at Day 1 will not continue to 12-month follow up. Crohn's Disease (CD) patients with no or mild disease activity at Day 1 but with colonoscopy or calprotectin levels (i.e, calprotectin >200ug/g) in the previous year suggestive of inadequate control of activity will progress to 12-month follow up.

Number of subjects

It is expected to include approximately 400 patients regardless of IBD type. This sample size will allow estimates with 95% confidence interval and a margin of error less than 5%.

Based on the above and considering an expected ratio of CD/UC of approximately 50%/50%, and that the rate of inadequate control of disease activity varies from 20-30% (regardless of the IBD type), it is expected to analyse 40-60 patients with CD and 30-50 patients with UC during the 12-month follow up.

Diagnosis/Disease/Condition and main criteria for inclusion

Subjects must meet all of the following inclusion criteria: 1) male or female subjects, 2) aged 18 years or older (at the time of diagnosis of moderate to severe UC or CD), 3) with diagnosis of moderate to severe CD or UC for at least 6 months prior to Day 1 appointment according the clinical or endoscopic criteria ^(23, 24, 25, 26, 27), 4) who provided the written

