6.3.4 Enrolment

Each Study Site Responsible (Investigator) should include consecutive subjects who meet eligibility criteria, from patients attending pre-scheduled routine medical appointments.

The expected recruitment of study subjects will occur during a 6 month period. A patient tracking log form will be used by each site.

Subjects should be included in the study only once. Data erroneously collected from subjects for which written consent is not available, will not be included in or will be deleted from the database.

After 2 and 4 months of enrolment, the overall proportion of patients with CD and UC will be reviewed. In case the expected ratio of IBDs (50%CD/50%UC) is not attained at 2 and 4 months of enrolment, the participating sites will be instructed to change future enrolments so

that this balance is achieved and that at least 30 UC patients and 30 CD patients with active disease enter the prospective follow-up.

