10.1.1 Study Endpoints

The main study endpoints are:

Primary Endpoints:

- For Crohn's Disease: Proportion of patients with active disease (HBI ≥ 8 or CDAI ≥ 220 points - based on criteria used by the site) at Day 1.
- For Ulcerative Colitis: Proportion of patients with active disease (9-point partial Mayo score ≥ 5) at Day 1.

Secondary Endpoints:

- Distribution of age, gender, smoking habits, professional status by IBD type.
- Distribution of clinical variables by IBD type.

- Therapies for IBD (aminosalicylates, steroids, immunomodulators, immunosuppressors, biologics, antibiotics, probiotics, surgeries) within the previous 3 years.
- Proportion of biologic-experienced patients.
- Proportion of patients who have not responded previously to biologic therapies and reason.
- IBD treatment introduced at Day 1.
- Socio-demographic, clinical and treatment-related variables in patients with moderate to severe activity of CD (HBI \geq 8 or CDAI \geq 220 points) versus patients with light or no activity (HBI $<$ 8 or CDAI $<$ 220 points).
- Socio-demographic, clinical and treatment-related variables in patients with moderate to severe activity of UC (partial Mayo score \geq 5) versus patients with light or no activity (partial Mayo $<$ 5).
- Among patients who had moderately to severely active CD at Day 1: HBI or CDAI score after 12 months.
- Among patients who had moderately to severely active UC at Day 1: Partial Mayo score after 12 months.
- Among patients who had moderately to severely active CD or UC at Day 1: Treatment after 12 months; in case of change of current treatment: reason for change
- Mean score of EQ-5D by IBD type.
- Mean score of different components of SF-36 by IBD type.
- Mean total score of IBDQ and by domain (bowel symptoms, systemic symptoms, emotional function and social function). The IBDQ is not validated for patients with ostomies and therefore should not be applied for these patients.
- Mean of subjects total percentage of work impairment (WPAI).
- Mean work time missed (WPAI).
- Mean impairment while working (WPAI).
- Mean total activity impairment (WPAI).
- Health resources (previous 3 years) imaging and laboratory testing, surgeries, hospitalizations, consultations and adverse events.

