10.2 Primary Analyses

For Crohn's Disease (CD), the proportion of patients with active disease at Day 1 will be presented as percentage and calculated as:

$$\frac{CD \text{ patients with } HBI \geq 8 \text{ or } CDAI > 220}{Total \text{ CD patients}} \times 100$$

For Ulcerative Colitis (UC), the proportion of patients with active disease at Day 1 will be presented as percentage and calculated as:

$$\frac{UC \text{ patients with partial Mayo score} \geq 5}{Total \text{ UC patients}} \times 100$$

The 95% confidence intervals will be computed for each estimate.

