10.6 Determination of Sample Size

It is expected to include approximately 400 patients regardless of IBD type. This sample size will allow estimates with 95% confidence interval and a margin of error less than 5%.

Based on the above and considering an expected ratio of CD/UC of approximately 50%/50%, and that the rate of inadequate control of disease activity varies from 20-30% (regardless of the IBD type), it is expected to analyze 40-60 patients with CD and 30-50 patients with UC during the 12-month follow up.

11 Reports

A Non-Interventional Study Report based on the results obtained will be prepared and submitted to Global Research for distribution. The Final Study Report should be available within one year from collection of the last data point, and the participating sites should be informed about the results when the report is finalized.

12 Publications

Takeda aims to have the results of this study published.

Takeda has the right to use the data and results for regulatory purposes and for internal presentation within the company and to partners.

13 Archiving of Study Documentation

During the course of the study the Site Responsible must as a minimum file the essential documents (Section 4.4), the protocol, any amendments, the list of participating subjects, the written informed consents, the CRFs and the progress reports in the Study Site File. After final database lock the Site Responsible must as a minimum store the list of participating subjects and the signed Informed Consent Forms on site for 5 years. The Site Responsible should store additional study documentation for a longer period of time as required by any local regulations and/or hospital requirement.

14 References

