## **5 ANALYSIS ENDPOINTS**

### **5.1 Primary Endpoints**

The primary endpoints of the study are:

- For CD: Proportion of patients with active disease (HBI  $\geq$  8 or CDAI  $\geq$  220 points – based on the criteria used by the site) at Day 1;
- For UC: Proportion of patients with active disease (9-point partial Mayo score  $\geq$  5 points) at Day 1.

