## **6 DETERMINATION OF SAMPLE SIZE**

However, it is expected to include approximately 400 patients regardless of IBD type. This sample size will allow estimates with 95% confidence interval and a margin of error less than 5%. Based on the above and considering an expected ratio of CD/UC of approximately 50%50%, and that the rate of inadequate control of disease activity varies from 20-30% (regardless of the IBD type), it is expected to analyze 40-60 patients with CD and 30-50 patients with UC during the 12-month follow up.

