## 7.5 Primary Analysis

The primary endpoint analysis will be performed calculating the proportion of patients with active disease at Day 1. The results will be presented as percentage and calculated as.

- For CD:

$$p_{CD} = \frac{\# \text{ patients with active } CD (\text{HBI} \geq 8 \text{ or } \text{CDAI} > 220)}{\# \text{ total of patients with } CD} \times 100$$

- For UC:

$$p_{UC} = \frac{\# \text{ patients with active } UC (\text{Mayo partial score} \geq 5)}{\# \text{ total of patients with } UC} \times 100$$

The 95% confidence interval will be computed for each estimate. In this study, the primary endpoint will be analyzed for cross-sectional dataset.

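### The margin of error below 5% holds only for the pooled 400 patients, not for the separate CD and UC primary proportions, and the expected UC follow-up number does not follow from its inputs

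*Protocol*

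**What the plan says.** Protocol 1.4, Protocol 10.6 and SAP 6 carry the same short sizing argument. About 400 patients are to be included, counted across both diseases. Protocol 10.6 continues: "This sample size will allow estimates with 95% confidence interval and a margin of error less than 5" per cent. The text does not say which estimate this margin belongs to.

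The primary endpoints are defined by disease. Protocol 10.1.1 lists a CD proportion and, separately, "For Ulcerative Colitis: Proportion of patients with active disease"; SAP 5.1 does the same ("For UC: Proportion of patients with active disease"). The formulas in Protocol 10.2 divide by all CD patients and by all UC patients respectively. On intervals, Protocol 10.2 says "The 95% confidence intervals will be computed for each estimate" and SAP 7.5 says "The 95% confidence interval will be computed for each estimate".

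The planned split is equal. Protocol 6.3.4 provides for sites to be redirected: "In case the expected ratio of IBDs (50%CD/50%UC) is not attained at 2 and 4 months of enrolment". It also asks for at least 30 patients with active disease in each group in the prospective phase.

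From the equal split and a 20-30% rate of inadequate control, said to be the same for both diseases, Protocol 1.4 concludes that "it is expected to analyse 40-60 patients with CD and 30-50 patients with UC during the 12-month follow up". SAP 6 repeats this: "it is expected to analyze 40-60 patients with CD and 30-50 patients with UC during the 12-month follow up".

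**The concern.** The only justification for the sample size in either document is a precision statement, and it describes a quantity that is not an endpoint. A reader would naturally apply the margin below 5% to the primary results, each of which rests on about half of the patients. No precision for CD or UC alone is given anywhere.

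The follow-up numbers are a second, separate problem. Equal group sizes and one common rate must give equal expected numbers, yet the printed ranges differ by 10 patients at each end.

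What is at stake is the accuracy of the stated precision and of the planning numbers. Neither point changes an analysis or biases an estimate.

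**Working it through.** **Inputs.** All come from Protocol 10.6 (repeated in Protocol 1.4 and SAP 6): N about 400, 95% confidence, CD/UC 50%/50%, active-disease rate 20-30% in both diseases. This gives 400 × 0.5 = 200 planned patients per disease. No method for the confidence interval is named, so three were tried.

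**Step 1: reproduce the plan's figure (n = 400).** The Wald half-width is 1.96 × √(p(1−p)/n).

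- p = 0.20: 1.96 × √(0.16/400) = 3.9 points
- p = 0.30: 1.96 × √(0.21/400) = 4.5 points
- p = 0.50: 1.96 × √(0.25/400) = 4.9 points

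The margin below 5% is therefore reproduced for the pooled sample, even at p = 0.50.

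**Step 2: apply it to the primary endpoints (n = 200 each).** Half-widths in percentage points (half the interval length):

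| Rate | Wald | Wilson | Clopper-Pearson |
|---|---|---|---|
| 20% | 5.5 | 5.5 | 5.8 |
| 25% | 6.0 | 6.0 | 6.2 |
| 30% | 6.4 | 6.3 | 6.6 |
| 50% | 6.9 | 6.9 | 7.1 |

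Every method exceeds 5 points over the whole 20-30% range. At n = 200 the Wald half-width equals 5 points when p = 0.154, so the rate would have to be about 15% or less, which is outside the plan's assumption.

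An unequal split does not help. In any division of 400 the smaller group has at most 200 patients, so its half-width is at least the value in the table.

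For reference, the number needed for 5 points is 1.96² × p(1−p)/0.05². This gives 246 patients per disease at 20%, 289 at 25% and 323 at 30%. Two groups at 20% would already need 492.

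**Step 3: expected follow-up numbers.**

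- CD: 200 × 0.20 = 40 and 200 × 0.30 = 60. The printed 40-60 is reproduced exactly.
- UC: 200 × 0.20 = 40 and 200 × 0.30 = 60. The printed 30-50 is not reproduced.
- Total, whatever the split: 400 × 0.20 = 80 to 400 × 0.30 = 120. The printed ranges add to 40 + 30 = 70 and 60 + 50 = 110.
- Worked backwards, UC 30-50 implies 30/0.20 = 150 to 50/0.30 = 167 UC patients, and CD 40-60 implies 200 CD patients. Together that is 350-367, not 400.

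A possible origin, as inference only: under the superseded 60/40 split in the amendment log, UC would be 160 × 0.20-0.30 = 32-48, which rounds to 30-50. The finding does not depend on this, because the mismatch lies within the current text.

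**The case against.** **The pooled figure is correct and is introduced as pooled.** The preceding sentence counts patients across both diseases, and the primary objective speaks of IBD patients as a whole. On this reading the per-disease precision is an omission rather than an error. That is fair as to the arithmetic of the sentence. But the endpoints, denominators and intervals are all per disease, so the one precision figure given describes neither primary estimate.

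**Little depends on it.** The study is descriptive, no test or decision rule is tied to 5 points, and the reported intervals will show the true precision. This stands and limits the importance of the point.

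**The equal split may not describe actual recruitment.** SAP 8 says the amendment took effect at the end of recruitment at one centre and after recruitment at the others, and it was this amendment that introduced 50/50. This also stands: 200 per disease is a planned number. It does not rescue the margin, since no split of 400 brings both diseases under 5 points at 20-30%.

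**The follow-up ranges may count patients analysed rather than patients entering.** Attrition could lower both diseases, while the CD-only entry route by colonoscopy or calprotectin (Protocol 6.3.1) could restore the CD number. For example, a 20% loss gives 40 × 0.8 = 32 to 60 × 0.8 = 48 in each disease, close to the printed UC range. CD would then need 8 to 12 extra patients to return to 40-60. This is possible, but neither an attrition rate nor a yield from the CD-only route is stated as a sizing input, and the CD range equals 200 × 20-30% with no adjustment. The sponsor may have such an assumption; if so, it needs to be written down.

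**Conclusion.** Both parts hold. The margin below 5% is correct for the pooled 400 but not for either primary endpoint. With about 200 planned patients per disease and a rate of 20-30%, the half-width is about 5.5 to 6.4 points (Wald), or 5.8 to 6.6 with exact intervals. The Wald excess over 5 points is about 0.5 to 1.4. These figures assume independent patients. Clustering within the roughly 20 sites could widen them, and the documents give no intracluster correlation with which to judge by how much.

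The UC follow-up expectation of 30-50 does not follow from the stated inputs, which give 40-60. This rests on the equal split and common rate as printed, with no attrition, since none is stated.

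The consequence is modest: no bias, no change to the analysis, and the minimum of 30 active patients per disease is met under either range. It should still be corrected, because this paragraph is the whole sample-size justification and it appears in both documents.

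**What to change.** Make the same two edits in Protocol 1.4, Protocol 10.6 and SAP 6.

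1. State the precision of the two primary endpoints. For example: with about 200 planned patients per disease, the half-width of the 95% confidence interval is about ±5.5 to ±6.4 points at rates of 20-30%, and ±6.9 points at 50%. Label the margin below 5% as applying to the pooled sample only.
2. Change the expected UC follow-up number to 40-60, or state the assumption that produces 30-50: a smaller UC group with a matching total, or an attrition rate. If attrition is the reason, say how it and the CD-only entry route lead to 40-60 in CD.

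The cost is wording in three places, with no extra patients and no change to the analysis. The only drawback is a slightly less favourable stated precision.

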## VERSION CONTROL

Version No.	Version Date	Author	Changes from Previous Approved Versions
0.1	03MAY2017	PPD	Not Applicable (First Version)
0.2	24OCT2017	PPD	

• Signature page: the sponsor responsible for SAP approval changed

• Inclusion of the section 9. DISCREPANCY IN RETROSPECTIVE DATA AFTER DATABASE LOCK

0.3	30JAN2018	PPD	

• Inclusion of the item 7) in the section 8. PROTOCOL CLARIFICATIONS/AMENDMENTS clarifying that in the longitudinal analysis a sensitivity analysis will be performed to determine the proportion of patients with active IBD after 12 months considering the activity disease assessment in a time window of 1 month

## LIST OF ABBREVIATIONS

BMI	Body Mass Index
CD	Crohn Disease
CDAI	Crohn's Disease Activity Index
CPI	Consumer Price Index
CRF	Case Report Form
EQ-5D	EuroQol-5D
HBI	Harvey Bradshaw Index
HR	Hazard Ratio
IBD	Inflammatory Bowel Disease
IBDQ	Inflammatory Bowel Disease Questionnaire
IRR	Incidence Rate Ratio
MS	Minimum Salary
OR	Odds Ratio
QoL	Quality of Life
SAP	Statistical Analysis Plan
SF-36	Short Form-36
UC	Ulcerative colitis
VAS	Visual Analog Scale
WPAI	Work Productivity and Activity Impairment Questionnaire

## 1 RATIONALE

This Statistical Analysis Plan (SAP) was written for Biostatistics and intends to provide guidelines from which the analysis will proceed, create a common and clear understanding of the planned analysis by all involved. This SAP was prepared by the biostatistician who will be further responsible (if possible) for the statistical analysis of the study data.

This SAP, in particular table shells and examples of figures/graphs, was reviewed and approved by the Sponsor's Representative previously to database locking and performance of the statistical analysis.

Any changes to the planned statistical methodology/definitions described on this SAP during the statistical analysis of the study data will be documented in the Statistical Report.

This document was written in accordance with the information contained in the Amendment 1 of Study Protocol Vedolizumab\_4008 of October 17, 2016 and CRF version 3.0, 11OCT2016.

This version of the SAP is an amendment of the SAP approved on May 03, 2017.

## 2 LITERATURE REVIEW

Inflammatory bowel diseases (IBD) comprise mainly Crohn's disease (CD) and ulcerative colitis (UC) (1). Signs and symptoms of active IBD may include abdominal pain, rectal bleeding, and fatigue. Treatment is not curative although it is generally effective in relieving symptoms (2). In some cases, surgery may be a solution but postoperative complications may occur, alongside with continued abnormal bowel function, and poor improvement in patient quality of life (QoL) (3).

With episodes of relapse and remission, IBD presents relevant health and economic burden (4,5). In fact, IBD impact on patient quality of life is particularly relevant since it affects mainly young individuals, may present severe symptoms and disease flares are unpredictable (6). Alongside with loss of patient's QoL, symptoms may also impact work productivity and increase the economic burden of these diseases (7).

Globally, the incidence of UC varies between 0.5-24.5/105 inhabitants, while CD incidence varies between 0.1-16/105 inhabitants worldwide; IBD prevalence is estimated to reach up to 396 per 105 people (8). The incidence of inflammatory bowel disease (IBD) has been increasing in several world regions, namely in developing countries (9,10).

In Brazil, epidemiologic and cost of illness information about IBD is scarce. Increased frequencies of outpatient visits and hospitalizations in the major urban centers of Brazil have been observed (11, 12,13). A retrospective hospital study in Piauí (North-eastern Brazil) with 252 IBD patients, observed that 152 (60.3%) were UC patients and 100 (39.7%) CD patients (14). More recently, a cross-sectional study in two IBD treatment referral centers in Bahia (North-eastern Brazil) has described

demographic and clinical characteristics of 267 patients with UC, being observed that extensive colitis was positively associated with male gender, diarrhea, weight loss, and a younger age at diagnosis (15). And there are no studies describing the health care resources and costs of IBD in Brazil.

Treatment of IBD remains challenging, with several strategies available (1,11). In Brazil, treatment options include salicylic derivatives [namely, sulfasalazine and mesalazine (5ASA)], corticosteroids, immunosuppressors (azathioprine, 6-mercaptopurine, methotrexate, cyclosporine), and biologic treatment options (infliximab, adalimumab and, more recently, vedolizumab) (12,13,14).

Corticosteroids (oral prednisolone 0.75-1mg/kg/day) are indicated to induce clinical remission in patients with active UC or CD of mild and moderate intensity. Clinical remission is achieved in 70%-90% of cases after 4-6 weeks of treatment but endoscopic and histologic remission are only achieved in approximately 30% of cases. In addition, corticosteroid-resistant and corticosteroid-dependent CD cases ranges from 8%-20% and from 15%-36%, respectively. In UC, reported frequencies of corticosteroid-resistance and dependence were 29% and <10%, respectively (12).

Regarding maintenance treatment, corticosteroids are not indicated due to side effects. Sulphasalazine and 5-ASA are recommended in the maintenance of remission of UC (11, 12). Immunosuppressors are effective in maintaining remission in CD and UC and while promoting corticosteroid withdrawal in corticosteroid-dependent patients (12). However, methotrexate is nowadays a second-line immunosuppressor for patients resistant or intolerant to azathioprine or 6-mercaptopurine, and cyclosporine seems to have no therapeutic value in treatment of CD (11).

Biological therapy has been increasingly used, namely for moderate to severe IBD or when there is no response to conventional treatments (12). In fact, infliximab (11,15), adalimumab (16,17) and vedolizumab (13,14) have shown to be effective in induction and maintenance of clinical remission of UC and CD. Side effects usually occur in less than 10% of cases, and it has been described that biological therapy can promote endoscopic and histologic improvement (12). Biologics have also the potential to improve QoL in IBD patients (18).

In face of IBD complexity and heterogeneity, treatment decision should consider the activity and severity level, the extension of inflammatory process and corticoid dependency (12). Furthermore, if the first-line immunosuppressive maintenance therapy fails, several other factors should be taken into account, including patient's wishes, fecundity and patient age (11).

